### 1.2.4. Summary of the team's qualifications

PI [name] is an exercise physiologist (EP) specializing in digital health, currently completing an NIDDK K01 on the development of an informatics-based digital intervention to promote physical activity by people with T1D. He has also collaborated on the psychometric development of the WANT model. Besides being PI of the above prior studies, he coordinated a randomized trial of 120 individuals as a postdoc64 and a smaller randomized trial for his doctoral dissertation. He furthermore brings extensive experience leveraging physical activity trackers for health purposes, including Veterans Affairs investigator-level funding and lead authorship of global stakeholder panels. His co-investigators on the present study include three of his mentors and one of his collaborators, all of whom he has published with extensively. [name] is a behavioral psychologist-scientist with additional expertise in digital health tools and using technology to improve treatment access and engagement. She is PI of an R-series award utilizing smartphone tracking to anticipate vulnerabilities to substance abuse and adverse mental health states. [name] is an endocrinologist-scientist, internationally recognized expert in continuous glucose monitoring, and PI of 10 awards from the U-, R-, and DP-3 series. **[name]** is an endocrinologist-scientist with expertise in exercise research. **[name]** is a biostatistician trained in epidemiology and recently focusing on methods for analyzing the circadian rhythmicity of continuous motor activity.

August 13, 2024 Version #7

# 2 Rationale/Significance

### 2.1 Rationale and Study Significance

### PRIMARY AIMS:

Current evidence-based T1D self-management interventions target glycemic control but ignore other modifiable health concerns prevalent in T1D such as hypertension and obesity. Exercise interventions could provide a novel solution if they could innovatively address the diabetes management and psychosocial challenges around exercise posed by T1D. Continuous glucose monitoring (CGM) allows patients and providers to comprehensively track the short- and long-term outcomes of exercise. Evidence-based interventions to translate CGM technology into sustainable adherence to exercise-related behaviors are lacking.

### SECONDARY AIMS:

Physical activity with T1D has been linked to glycemic destabilization and fear of hypoglycemia, but there is a need to determine real-time mechanisms underlying this link. Fear of hypoglycemia has been measured as a "trait" (i.e., personality-specific) but in just one study as a "state" (i.e., situation-specific). Participants reported their state fear of having hypoglycemia over the next 12hr. Responses had significant intraindividual variation and correlation with the related construct of blood glucose variability, indicating the need to further study fear of hypoglycemia as a state variable. Glycemic destabilization meanwhile is recognized to cause intense symptoms that acutely preclude physical activity, but no study has addressed the possible impact of more nuanced changes. E.g., downward-trending glucose could affect motivation to be active even if not projecting an excursion outside the clinically safe range.

Addressing this weakness, we and others have begun demonstrating that such affective (i.e., automatic) feeling states are the primary motivational factors driving humans to engage in physical activity. Furthermore, these motivational factors have highly transient effects, exhibiting more state than trait qualities. Therefore, we must test these real-time states to link T1D-related barriers to physical activity (Figure 2 in section 1.1).

### 2.2 Risks

**Confidentiality:** Due to the collection of private identifiable information, there is a possibility of a security breach compromising subject confidentiality. Such breaches are extremely uncommon when proper IRB-approved precautions are taken.

Several steps will be taken to safeguard the confidentiality of subjects and their data. All research data collected outside of the mobile applications will be assigned a study participant number and that number will only identify participants in digital databases on REDCap or Actigraph Actilife software (downloads Actigraph GT9X blinded hip & wrist watch). Audio-recorded interviews and orientation sessions will be transcribed and names, places, and any other identifying information will be removed. The names of participants will not be associated with this data and assessments will be maintained according to participant study number. A master list connecting participant study numbers to participant names will be kept on a secure server where it can only be accessed by senior level project staff. Any information published as a result of the study will be such that it will not permit identification of any participant.

August 13, 2024 Version #7

All research data that is collected via the mobile applications (CGM, diary responses, exercise performance, insulin usage, carbohydrates, GPS) will be stored on the relevant web application programming interface (API) platforms (Dexcom, Fitbit, GlucoseZone), researcher dashboard (Ilumivu, Qualtrics), or user dashboard (InPen) in accord with Yale Information Technology Services protocols (Table A1). After syncing the data, the data will be immediately deleted from the participants' biosensor devices and smartphones. Web-based application and user sessions are encrypted between the server and client browser through the use of industry standard SSL certificates. As soon as each participant completes the study protocol, their data will be immediately transferred from the API platform to Yale secure servers by secure file-protection strategies, assigned to the de-identified participant study number noted in the previous paragraph, and deleted from the API platform. All data is encrypted both at rest and in transit.

Device	Identifiers	Data Capture	Data Export to Yale Server for Deidentified Analysis
Actigraph GT9X Blinded Watch	None	Physical hookup to computer desktop with Actilife software	From Actilife Software

Right to privacy for participation in this research will be protected through alphanumeric coding of data (in place of names) and proper storage of research records, including interviews and data downloaded from the web API platforms. Collected materials will be maintained via an alphanumeric reference system maintained by [name]. Participants' names will appear only on the consent form, the HIPAA authorization form, and a master list maintained on REDCap that is separate from research data. Our data collection and management procedures are fully compliant with HIPAA. Access will be limited to personnel intimately involved in the study. Electronic data will be deidentified and password protected. Only members of the study team will have access to the physical or electronic data.

**Hypoglycemia:** There is risk of hypoglycemia due to exercise. The magnitude of these events can range from a few minutes of mild symptoms (e.g., dizziness, fatigue) to prolonged severe symptoms (e.g., loss of consciousness, diabetic ketoacidosis).

The T1D standard of care recognizes the probability of these events as common in the context of daily living. Our previous pilot studies exercise for T1D (c.f. sect 1.2.1, 1.2.2) had some episodes of mild hypoglycemia around exercise, but they quickly resolved following appropriate rescue carbohydrates and there were no severe episodes, ketoacidosis, or other adverse events.

We will apply the same safety protocols to minimize these risks in the current study. To ensure safety, all participants will receive clearance to participate in the exercise by one of the study endocrinologists Drs. [name] or [name]. They will self-monitor their blood glucose using a CGM. Those without their own monitor upon study entry will have one provided. CGM has reduced risk of hypoglycemia during and after exercise in randomized controlled trials compared to usual care (reviewed in).

They will also be provided a comprehensive exercise safety orientation which is detailed in Appendix 22a. Briefly, the information includes review of devices, supplies, space, safe glucose ranges and carbohydrate snacking for exercise, reminders from CGM training pertinent to exercise, insulin adjustments around exercise, watching for symptoms, and who to call with concerns. They will be provided and instructed to keep carbohydrate-containing foods and drinks (eg, orange juice, glucose tablets) available to use when indicated by glucose testing or symptoms. In addition, they will be educated regarding the American Diabetes Association guidelines for self-monitoring blood glucose and urine ketones, if indicated, and appropriate adjustments of diet and insulin before, during, and after engaging in exercise. For instance, if blood glucose is less than 90 mg/dL, they can consume 10-20g of fast-acting carbohydrates (eg, 4 oz of orange juice or 3 glucose tablets) and wait to commence with exercise until blood glucose is confirmed to be above 90 mg/dL. If blood glucose is greater

Protocol Number 2000035846

August 13, 2024 Version #7

than 270 mg/dL and not associated with a recent meal, they must check their blood for ketones and avoid exercise if they have ketones ≥1.0 mmol/L.

Participants will be encouraged to be vigilant for symptoms of hypoglycemia during exercise and for the remainder of the day because exercise increases the risk for nocturnal hypoglycemia. The symptoms they will be encouraged to be vigilant for include cold, clammy skin, pallor, difficulty concentrating, shakiness, lack of coordination, irritability, hostility, and poor behavior, a staggering gait, fatigue, nervousness, excessive hunger, headache, blurred vision and dizziness, and abdominal pain or nausea. In these instances, they will be advised to refrain from exercise while checking blood glucose.

Participants will be monitored for exercise-associated events (hypo- and hyperglycemia, diabetic ketoacidosis, other health risks) as detailed in the Data and Safety Monitoring Plan (Sect 8.7). In brief, a research staff member will daily review each participant's CGM data, fingerstick glucose tests, ketone tests, exercise start times, and diary records of hypoglycemia and other clinical events (see Data and Safety Monitoring Plan "Tracking" section) each of the first 14 days of the trial for each participant. Instances of severe hypoglycemia, diabetic ketoacidosis, a missed ketone test, or other clinical event will result in immediate discontinuation of exercise until a physician has alerted the participant and the participant's primary diabetes care provider to the issue and developed a prevention strategy, consulting with the primary diabetes care provider as needed. For instances of a missed test, physician contact can be replaced initially by research assistant contact to query symptoms and troubleshoot testing procedures, followed by physician contact if symptoms were present.

The principal investigator [name] and a study physician (Drs. [name] or [name]) will review the above data plus carbohydrate and insulin dosing around exercise, every 2 weeks during the clinical trial. Participants exhibiting patterns confirmed by the physician to be indicative of problematic exercise-induced hypo- or hyperglycemia will be alerted to the issue and referred to their diabetes care provider for follow-up (all patients will submit provider information to the study team at study start). [name] will join at least every other occurrence of these meetings (i.e., at least every 4 weeks) and provide a second review of [name] medical management decisions. Participants will be trained in allowing their provider to access their CGM data. Mild hypoglycemia will not be exclusionary since such individuals are in high need of exercise intervention. Any day-to-day decisions about clinical care, including adjustment of insulin dosing or CGM target ranges will be made by the participant's provider, not the study physicians. Clinical providers will not monitor CGM in real-time.

All participants participate in routine follow-up, consisting of quarterly visits to the clinic and 24-hour access to nurse and/or physician consultation. It is not anticipated that any of the data collection procedures or the intervention will cause any adverse effects. Nonetheless, the participants will continue to receive routine medical and nursing care throughout the study period, and intervention for adverse effects will be available.

These protocols have been utilized by Drs. [name], [name], and [name] over four prior exercise clinical trials among youth and adults with T1D that had no instances of severe hypoglycemia or diabetic ketoacidosis (HIC #s 1605017843, 2000025992, 2000030105, 2000033736).

**Hyperglycemia:** There is a risk of hyperglycemia due to exercise from factors such as counterregulatory hormone response releasing glucose into the blood.

See above regarding blood glucose testing, blood glucose monitoring review by research staff, Drs. [name], [name], [name], and routine clinical support. Regarding hyperglycemia

August 13, 2024 Version #7

specifically, participants will be encouraged to be vigilant before, during, and after exercise for signs or symptoms of hyperglycemia such as dry mouth, headache, heaviness, pressure behind the eyes, or unusual increase in thirst. They will be advised in these instances to reassess their blood glucose. If blood glucose is greater than 270 mg/dL and not associated with a recent meal, they should check their blood for ketones and avoid exercise if they have ketones ≥1.0 mmol/L.

**Severe hypoglycemia and hyperglycemia:** There is a risk of severe hypoglycemia or hyperglycemia due to exercise.

Severe hypoglycemia will be defined as any blood glucose level resulting in symptoms which require outside intervention to control (including but not limited to confusion and loss of coordination). Severe hyperglycemia will be defined as blood glucose >500mg/dL, presence of urine ketones or other signs and symptoms of diabetic ketoacidosis (including but not limited to weakness and fatigue, confusion, shortness of breath). Patients will be asked to contact emergency services should these events occur. Specifically, Yale-affiliated patients with T1D have access to a 24-hour hotline with access to nurse and/or physician advice or can choose to call 911. Non-Yale-affiliated patients will be asked to call 911 or contact their providers' after-hours staff (all patients will submit provider information to the study team at study start). The study team will be notified of the event within 24 hours via daily diaries; moreover all participants will have the PI's direct contact information should they choose to contact him earlier by phone or email. Our team will then notify the patient's primary diabetes provider (if not already notified) and all study-related exercise will be suspended until patient receives further advice from their diabetes provider regarding next steps which may include modified exercise routines or suspension of the study altogether. All serious adverse events such as severe hypoglycemia and hyperglycemia will be reported to the PI verbally within 24 hours of study staff being notified and to university's IRB committee in writing within 5 business days. In the case of >1 episode of severe hypoglycemia or 1 episode of diabetic ketoacidosis not closely related to pump site failure, the participant will be removed from the study and referred to their diabetes care provider for follow-up.

**Exercise-related injuries:** Exercise may cause muscle soreness/pain, muscle strain, cardiovascular events, and tiredness during or after the activity.

The probability and magnitude of such injuries varies based upon factors such as the individual participant's fitness level and the difficulty of the exercise routines. Our previous pilot studies (sect. 1.2) had no injuries or muscle strains. The American Heart Association Scientific Statement notes that the frequency of exercise-related out-of-hospital cardiac arrest among the general population ages 35-90yr was measured at 3.0 per 100,000 person-years.

To minimize the risk of injuries or strains, participants will complete the GlucoseZone videos warm-up and cool-down routines. In addition, they will be coached to initially select classes from the "beginner" category and "short" to "medium" duration (15-40 minutes).

Though risk of serious injury is minimal, the research assistant will ask the participant weekly if they are having any of the symptoms overviewed on the consent form or any other injuries that could be made worse by exercising. In the event of positive responses, exercise physiologist (EP) [name] will contact them to ask follow-up questions, following protocols from the American College of Sports Medicine, to determine if they are indicative of pathology. If they are, [name] will report the episode to study physician [name] and the participant's own PCP and suspend the participant's exercise participation unless receiving PCP clearance to continue.

August 13, 2024 Version #7

**Study questionnaires and interviews:** Participants may experience some distress when discussing factors important to diabetes, diabetes management, and psychosocial stressors.

The probability of such responses is uncommon and the typical magnitude of responses is mild. No such instances were reported in our previous pilot studies (sect. 1.2).

Research participants who report negative psychological reactions to the research protocol, or negative emotional reactions to diabetes elicited during participation in the research study, will be referred to their regular clinical provider. If research staff determine that the degree of psychological reaction is severe, the physician staff of the study ([name] or [name]) will be contacted to assess the participant and determine whether acute urgent referral is needed.

**Continuous glucose monitoring (CGM):** Participants will use Food and Drug Administration (FDA) approved Dexcom G6 CGM as part of the American Diabetes Association standard of care. There is a low risk of developing a local skin infection at the site of the sensor needle placement. Itchiness, redness, mild bleeding, and or bruising may occur at the insertion site. Participants may develop localized reactions to adhesive used to secure the sensor.

Risks of glucose sensor insertion will be minimized because participants will be instructed to cleanse skin aseptically prior to insertion. Participants will receive training on sensor use if they have not used the sensor previously.

**Fitbit:** In a very small number of participants (~3% in a recent report) the Fitbit may contribute to skin irritation or allergies. To minimize this risk, participants will be trained in manufacturer guidelines including keeping it dry, not wearing it too tight (loose enough that it can move back and forth on the wrist, moved 2-3 finger widths above wrist bone during exercise only), and giving the wrist a rest by removing the band for an hour every couple of days.

There are no potential social, cultural, financial, or legal risks to participants consenting to participate in this investigation.

**Overall assessment:** The risks associated with the current study are greater than minimal because exercise presents risk of hypoglycemia, hyperglycemia, and injuries. However, the exercise routines are within the scope normally performed by adults with T1D or other absolute insulin deficiency diabetes during daily living and the participants will benefit from our protocol measures described above that minimize exercise risks. In addition, the information to be gained will help develop an intervention supporting adults with T1D or other absolute insulin deficiency diabetes to become more physically active and overcome these risks of usual activity. Therefore, the value of the information to be gained outweighs the risks involved.

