Weather (temperature, humidity, windchill for GPS location by National Weather Service)	Momentary value	Weekly averages

August 13, 2024

Version #7

Physical Activity Daily Intention  multiple choices (exercise in morning, occupational activity, etc  )	Daily state	Weekly frequencies
Competing Demands "How busy is today's schedule?"82	Daily state	Weekly averages
Illness "Were you sick yesterday?"	Daily state	Weekly frequency
Sleep (total, waketime after sleep onset)**	Daily state	Weekly averages

††Dependent variable for aim 2-1. For aim 2-2, this is an independent variable and the dependent variable is Actigraph-measured physical activity. \*Validated in ref for 5-item versions and ref for 1-item versions. †1-item is emerging new instrument and 18-item widely validated ( $\alpha$ =.89). ††1-item parallels fear of hypoglycemia item one row up, and 24-item is validated ( $\alpha$ =.92). ‡Assessed by Dexcom G6 continuous glucose monitor (mean error 9%-10%). Quantified as consensus metrics (Coefficient of variation, mean, time in target range [70-180 mg/dL], time above range, time below range i.e. hypoglycemic). §.41-.88 convergent validity. ||assess at wakeup and apply to all timepoints that day. \*\*Assessed by Actigraph GT9X. Each 60-s epoch will be scored as wake or sleep (Sadeh's algorithm).

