Daily morning survey that captures daily morning context during app intervention is started at this visit -- Appendix 8a: 1) prior day hypoglycemia episodes; 2) recent clinical events (asked every day for 2 weeks, then every 2 weeks); 3) fear of hypoglycemia previous night and coming day; 4) sleep quality and nocturia previous night; 5) competing demands and exercise plan for the day.

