#### Data Captured by App

**Daily context each morning -- Appendix 8a:** 1) prior day hypoglycemia episodes; 2) recent clinical events (asked every 2 weeks only); 3) fear of hypoglycemia previous night and coming day; 4) sleep quality and nocturia previous night; 5) competing demands and exercise plan for the day.

Pre- and mid-exercise context captured in conjunction with videos – Appendix 8b & 8c and passive data from app and sensors:  $\underline{1}$ ) carbohydrates taken;  $\underline{2}$ ) insulin dosing;  $\underline{3}$ ) weather;  $\underline{4}$ ) day of the week;  $\underline{5}$ ) exercise instructional video selected; 6) exercise performance metrics.

**24hr passive data from sensors –** 1) Continuous blood glucose; 2) Physical activity outside of exercise videos

The app uses this biometric data to give exercise guidance, as described in the funded grant submission (1K01DK129441) and below

Tool #1: Access to a library of 200 exercise videos following brief human orientation consultation (Appendix 18b). Our ~200 exercise videos (GlucoseZone™, New Haven, CT) include a combination of aerobic, resistance, flexibility, and balance exercises, in accord with American Diabetes Association recommendations. They can be filtered by difficulty level, duration, type of exercise (aerobic vs. resistance), muscle groups, mobility limitations (knee-friendly, shoulder-friendly, chair-based), indoor/outdoor, and home equipment availability. Using these filters, participants can select single sessions or 30-session series that progress in difficulty and duration. Participants self-schedule exercise time in their home environment or outdoor guided walking routes. Participants may select routines requiring no equipment, use a \$10 set of resistance bands we recommend, use their dumbbells or household items like frozen water bottles. A trained exercise physiologist (EP) from the research team ([name],) will guide downloading the app, discuss exercise levels, goals and safety (Appendix 22a), and recommend starting videos and series. This orientation will be audio-recorded and combined with later interviews for qualitative analysis (Sect 7.2.1, hypothesis 2-3). A consultant from the manufacturer of GlucoseZone (Fitscript LLC; [name] [name] or [name]) will be available for assistance with downloading, navigating, or troubleshooting the app.

August 13, 2024

Version #7

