We will detect any other exercise-associated health risks within 24-36hr and suspend exercise until a personalized preventive strategy can be formed. To achieve this level of monitoring, the morning survey question about prior day's clinical events (Appendix 8a, last question) will be asked of participants and monitored by research staff daily. If the participant reports a clinical event, the PI will complete Adverse Event review and summary (c.f. Protocol Sect 6.3) the same day (i.e., within 24-36hr of the reported event). If the event may be exercise-related, the participant will be informed to immediately suspend the exercise program (app account will be suspended) until the participant has been contacted by a study physician. The physician will alert the participant to the issue and develop a prevention strategy, consulting with the participant's primary diabetes care provider as needed. The exercise suspension will then be lifted, unless the participant has met the protocol's stoppage criteria.

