# **Steps to Minimize**

Among enrolled subjects, steps will be taken to minimize risks of hypoglycemia and hyperglycemia as detailed in section 2.2, "Protection against Risks". Briefly, these include

August 13, 2024 Version #7

instructions to participants regarding safe blood glucose testing habits, regular tracking of hypoglycemia and hyperglycemia as described above, blood glucose monitoring review by Drs. [name] and [name] every 2 weeks with clinical referrals by [name] as appropriate, second check of [name] medical management decisions by [name] at least every 4 weeks, and routine clinical support. Regarding non-glycemic medical issues related to older age (e.g., angina history), [name] will be available for consultations.

Participants will be instructed to call the Yale 24-hour access to nurse and/or physician consultation or 911 if they have any instances of severe hypoglycemia, diabetic ketoacidosis, or other severe clinical event. Non-Yale-affiliated participants will be required to submit information regarding their providers and will be instructed to call 911 if they do not have access to 24-hour consultation and experience an adverse event. Any such instances noted on participant diary surveys will be reviewed by our study team and forwarded to their diabetes provider. Patients will be instructed to suspend exercise until they have a chance to connect with their provider who will then determine the next steps regarding resumption of exercise and ongoing mobile application usage. Any day-to-day decisions about clinical care including adjustment of insulin doses or CGM target ranges will be made by the participant's provider, not the study physicians.

These protocols have been utilized by Drs. [name], [name], and [name] over four prior exercise clinical trials among youth and adults with T1D that had no instances of severe hypoglycemia or diabetic ketoacidosis (HIC #s 1605017843, 2000025992, 2000030105, 2000033736).

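### Section 2.2 promises 24-hour diary notice of severe hyperglycemia and ketoacidosis with no end date, but the diary item that could report them goes from daily to fortnightly after two weeks

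*Combined protocol and SAP*

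**What the plan says.** Section 2.2 (Risks, severe hypoglycemia and hyperglycemia) defines severe hyperglycemia to include signs of ketoacidosis. It then states for both kinds of event: "The study team will be notified of the event within 24 hours via daily diaries". No period is attached. On that notice, the team informs the diabetes provider and suspends study exercise. Section 8.7 (Steps to Minimize) also relies on the diary for severe hypoglycemia, ketoacidosis and other severe events: "Any such instances noted on participant diary surveys will be reviewed by our study team and forwarded to their diabetes provider".

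The diary schedule is in Section 6.1.1. The morning survey starts at Visit 2 (Day 8). Its hypoglycemia item is daily. Its clinical-events item is described at Visit 2 as "recent clinical events (asked every day for 2 weeks, then every 2 weeks", and at Visit 4 (Day 22), when the app and the exercise program start, as "recent clinical events (asked every 2 weeks only".

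Section 8.7 (Tracking A) uses "the morning survey question about prior day's clinical events" for daily safety monitoring, under a heading that limits this to the first two weeks. The hypoglycemia paragraphs of Section 2.2 limit daily staff review to "each of the first 14 days of the trial for each participant". The 24-hour sentence carries neither limit.

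**The concern.** The 24-hour sentence is a safety commitment that starts an action, and one ketoacidosis episode not explained by pump site failure is a criterion for removal (Sections 2.2 and 6.5). If no diary item asks about such an event the next morning, the diary cannot deliver the notice. The team then depends on the participant choosing to call, on the next visit, or on a fortnightly review. The 150-minute weekly exercise target runs through follow-up (footnote to Table 1), so the exposure continues after the daily asking has ended.

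What is at stake is the study team's own response: contacting the provider, suspending exercise, and applying the removal rule. No efficacy or feasibility endpoint depends on it.

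**Working it through.** The plan's own figure is notice within 24 hours by diary. The check is whether the listed survey schedule can produce it.

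**Inputs**
- Exercise starts at Visit 4, Day 22; participation ends at Visit 10, Day 64; visit windows are ±7 days (Table 1).
- The clinical-events item is daily for two weeks from Visit 2 (Day 8), then every two weeks (Section 6.1.1).
- Event days are Days 22 to 63, so that each has a next morning by Day 64: 63 − 22 + 1 = 42. Of these, 28 fall in the app period (Days 22 to 49) and 14 in follow-up (Days 50 to 63).

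**Rule:** an event day d is covered if the item is asked on the morning of day d + 1.

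**As written, nominal visit days**
- Daily asks on Days 8 to 21, then Days 35, 49 and 63: covered event days are 34, 48 and 62.
- Daily asks on Days 9 to 22, then Days 36, 50 and 64: covered event days are 35, 49 and 63.
- Either way 3/42 = 7.1%, made up of 2/28 in the app period and 1/14 in follow-up. Any phase of a 14-day cycle gives 3.

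**As written, with visit windows:** shifting Visits 2 and 4 within the ±7 days, in the combinations tried, gives 3 to 8 of 42.

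**If the daily two weeks count from the start of exercise**
- Daily asks on Days 22 to 35, then 49 and 63: 15/42 = 35.7% (14/28 + 1/14).
- Daily asks on Days 23 to 36, then 50 and 64: 16/42 = 38.1% (15/28 + 1/14).

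No reading tried comes near 42 of 42.

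**Item wording.** Section 8.7 describes the item, in the daily period, as asking about the day before. If that wording stays when the item goes fortnightly, 42 − 3 = 39 event days are never asked about. If it asks about the time since the last survey, every day is covered eventually, with a wait of up to 14 days at nominal timing.

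**Other routes to the team, set against 24 hours**
- Daily illness question ("Were you sick yesterday", Table 2): non-specific, an analysis covariate, and not named in the safety monitoring plan.
- Daily dashboard monitoring (Section 6.1.1, Tool #2): its stated purpose includes exercise safety, but it refers back to Section 8.7, where daily tracking is headed as the first two weeks and the alert signals are tied to exercise with a one-hour margin.
- Direct contact with the principal investigator (Section 2.2): at the participant's choice.
- Symptom and adverse-event checks at visits (Table 1): weekly, ±7 days.
- Review of glucose and ketones by the principal investigator and a study physician (Sections 2.2 and 8.7): every two weeks.

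Each helps; none is a daily diary and none guarantees 24 hours.

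**The case against.** The strongest reply is that the count measures survey asks rather than notice. Tool #2 has staff look at the dashboard daily, and Section 8.7 says that the dashboard holds glucose and ketones. A very high glucose or a positive logged ketone test could therefore be seen within a day during the app period. This stands as partial cover, so a reader must not infer from 3 of 42 that about 93% of such events would go unnoticed for days; the documents do not support that. It does not make the sentence true, because the route is not the diary and it defers to tracking that is exercise-linked and limited to two weeks.

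Second, the two weeks in Section 8.7 make best sense from the start of exercise, since the monitoring uses exercise start and stop times and suspension of the app account. That is a fair reading, and it is why 15 to 16 of 42 belongs beside 3 of 42. The Visit 2 and Visit 4 texts support the other reading, so the plan is ambiguous.

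Third, a reader might infer that nobody watches the data in the last 14 days because the app row in Table 1 ends at about Day 50. The documents do not say this: glucose sensing and the morning survey run to Visit 10, and Section 7.6 has diaries monitored daily with no end date. Nor do they say that the daily dashboard check continues. The point is open.

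Fourth, the two-week limit on daily review is disclosed elsewhere, and diaries were the lowest-rated of the listed components in the pilot (2.2 of 5), so thinning an item has a rationale. Both are true; neither limits the Section 2.2 sentence, and one yes/no item is a small burden.

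**Conclusion.** The concern holds in a limited form. For ketoacidosis and severe hyperglycemia, the unlimited 24-hour diary statement does not follow from the diary schedule once daily asking ends. A next-morning ask follows 3 of 42 event days as written at nominal visit days (3 to 8 under the windows tried), or 15 to 16 of 42 if the two weeks run from the start of exercise.

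This rests on the item lists in Section 6.1.1. Appendices 8a to 8c and 22b were not available, and another item there could change the finding.

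The statement does hold for severe hypoglycemia, which keeps a daily item. A reader might also infer that participants are left without care; the documents say otherwise. They are told to contact emergency services, and "Patients will be instructed to suspend exercise until they have a chance to connect with their provider". Few events are likely: four earlier trials using these protocols had no severe hypoglycemia or ketoacidosis, and exposure here is at most 24 × 42 = 1,008 person-days. It is a safety statement worth correcting because the correction is cheap, not a threat to the trial's conclusions.

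**What to change.** Preferred: ask the existing clinical-events item every morning through Day 64, worded to cover the time since the last survey, with daily staff review. Align the Visit 2 and Visit 4 descriptions in Section 6.1.1 and Tracking A in Section 8.7. A next-morning ask then follows 42 of 42 event days. The cost is one survey setting, one wording change and 42 − 3 = 39 extra yes/no answers per participant (26 to 27 if the daily two weeks already run from the start of exercise). The morning survey already goes out through Visit 10, and diaries are already monitored daily (Section 7.6).

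Otherwise, revise Section 2.2 so that 24-hour diary notice is claimed for severe hypoglycemia and, for ketoacidosis and severe hyperglycemia, only while the item is asked daily. Say that later notice depends on participant contact, the next visit or the fortnightly review. Do not state a number of days: the ±7-day windows can stretch the visit interval, and prior-day wording could mean that the fortnightly item never asks about the event. This costs a sentence or two but leaves the gap in place.
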